3.2 Study Endpoints

3.2.1 Primary Efficacy Endpoint

• OS, defined as the number of days from date of randomization to date of death.

3.2.2 Secondary Efficacy Endpoints

- EFS defined as the number of days from randomization to the earliest date of, treatment discontinuation (for reasons other than initiation of HCT), start of alternative anti-leukemia therapy (except for HCT), or death.
- Survival rate at 1 year after randomization. (Subjects will also be followed long term to estimate 2-year survival rate.)

- NDAOH.
- Transfusion independence rate, calculated based on the number of subjects with neither red blood cell (RBC) nor platelet transfusion for any period of 8 weeks after treatment.
- CR rate based on modified International Working Group (IWG) 2003 AML Response Criteria and CRh rate as described in the US FDA approved Prescribing Information of enasidenib and ivosidenib.
- CRc (CR+CRi+CRp) rate.
- HCT rate. (In subjects who undergo HCT, time to stem cell engraftment and 100-day mortality rate post HCT will also be assessed.)
- Duration of combined CR and CRh, defined as the time from first CR or CRh to time of relapse.
- Health-related QOL by EQ-5D (consisting of the EQ-5D-5L descriptive system and the EQ visual analogue scale [VAS]).

3.2.3 Safety Endpoints

Safety was assessed by subject-reported and investigator-observed AEs and 30- and 60-day allcause mortality, along with clinical laboratory tests (hematology, chemistries), concomitant medications, physical examination, vital signs, ECOG performance status, and ECGs.

4.0 SAMPLE SIZE

In order to provide power of at least 90% to detect a difference in hazard ratio of approximately 0.692 (median OS of 4.5 months for the TC arm versus 6.5 months for the guadecitabine arm) using a stratified 2-sided log-rank test at an overall 0.05 alpha level given the 1:1 randomization, the trial will require 315 death events. Assuming that the enrollment would be non-uniform over an 18 month period during which 3 to 29 subjects per month (3, 6, 9, 12, 15, 18, 21, 24, 27, and 29) were expected to be enrolled in the first 10 months in increasing order followed by 30 subjects per month in months 11-18, with the proportion of subjects dropping out each month equal to 0.012, then approximately 404 subjects would need to be randomized. If after a follow up of 12 months from the last patient randomized, the 315 death events had not occurred, the primary analysis would be conducted at 12 months from last subject randomized (if 277 or more death events have occurred), or after at least 277 death events had been observed (corresponding to 86% power). Based on DMC recommendation to stop further enrollment, the time of primary analyses was shifted to occur after approximately 12 months follow-up from the last subject randomly assigned to treatment or after the last subject is off study.

5.0 ANALYSIS SETS

5.1 Efficacy Analysis Set

Efficacy analyses will be based on intent-to-treat (ITT) principle. The Efficacy Analysis Set will include data from all subjects randomly assigned to study treatment. All data will be included and no subjects excluded because of protocol violations. For the analysis of efficacy data, subjects will be included in the treatment group according to their randomly assigned treatment.

For NDAOH, and health-related QOL by EQ-5D-5L, the primary analysis will include only the data collected during the first 6 months of the study because, during this study period, subjects are assessed monthly whether or not they are still on study treatment. Secondary analysis, if performed, may also include data beyond the first 6 months of the study (eg, over the entire study period until disease progression).

5.2 Safety Analysis Set

The Safety Analysis Set will include data from all subjects randomly assigned to study treatment who receive any amount of study treatment or any component of a multi-dose study treatment regimen. All data will be included and no subjects excluded because of protocol violations.

For safety data analysis, subjects will be included in the treatment group according to the treatment they actually receive. If a subject receives more than one type of study treatment during the study, the subject will be included in the treatment group according to the treatment received most frequently. In the unlikely event a subject receives the same number of cycles of two different treatments the subject will be included in the treatment group according to the treatment received first.

6.0 SCHEDULE OF ANALYSES

Data listings and summary tables were reviewed by the DMC approximately every 6 months to ensure the safety of study subjects and to enhance the quality of trial conduct (refer to protocol Section 4.4 and the DMC Charter). These data listings and summary tables were generated by

Axio Research LLC, an independent contract research organization (CRO) supporting the DMC activities.

One formal interim analysis of OS was planned to be conducted by the DMC when approximately half of the required 315 death events have occurred.

At the Sponsor's request, an additional earlier interim analysis of futility was conducted by the DMC at one of the scheduled DMC meetings on 12 September 2018 when approximately onethird of the required 315 death events had occurred. This interim analysis was added due to the emerging information showing a lack of significant survival benefit over the TC arm (similar to the Low Intensity TC in this study) from a similar trial conducted by the Sponsor in treatmentnaive AML subjects using the same drug product in which the study failed to meet the primary endpoint (SGI-110-04 study). This meeting resulted in a DMC recommendation to the Sponsor that enrollment in Study SGI-110-06 should be discontinued based on futility.

Since the enrollment was stopped prior to reaching the planned number of death events for the formal interim analysis of OS as described in the protocol, the formal interim analysis was cancelled.

7.0 STATISTICAL ANALYSIS

Unless otherwise specified, treatment comparisons will be performed between the guadecitabine group and the TC group. Additional comparisons of guadecitabine with each TC option in the patients randomized under that preselected TC option may be performed as appropriate. Procedures will be employed to control the alpha error associated with testing multiple endpoints (see Section 7.3.3). The statistical test to be employed for each comparison is specified below. The SAS® statistical package (SAS Institute Inc., Cary, NC, USA, version 9.4 or a later version) will be used for the analyses.

The following data listings by study center and subject will be provided, as recommended by the ICH E3 guideline "Structure and Content of Clinical Study Reports": discontinued subjects, important protocol deviations, demographics, individual efficacy data, subjects excluded from the efficacy analysis, AEs, medications, and the relevant laboratory measurements. Additional data listings may be generated to support other relevant discussions in CSR.

The baseline value for a particular variable is generally the last value collected prior to the Cycle 1 Day 1 (C1D1) study visit. For subjects who were randomized but did not receive study treatment, the baseline value is defined as the last value collected prior to randomization. For variables collected on Day 1 of Cycle 1 (C1D1) without explicit timing, the C1D1 values will be used as the baseline values since the protocol requires these tests or procedures to be performed prior to dosing.

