6.1 Randomization

Eligible subjects will be randomly assigned to study treatment. Treatment assignments for the individual subjects will be determined through a computer generated randomization scheme and accessed through an interactive response system. Instructions for access and use of the interactive response system for randomization will be provided to participating study centers separately.

Randomization will be 1:1 between guadecitabine and TC groups, and will be stratified by intensity of preselected TC option (high intensity vs low intensity vs BSC), ECOG performance status (0-1 vs 2), baseline cytogenetics (poor risk vs other; see Appendix 3), and study center region (North America vs ROW).

Selection of 1 of the TCs must be made prior to the randomization of each subject. Subjects should receive study treatment as soon as possible after randomization (maximum of 1 week between randomization and treatment).

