6.2 Blinding

The sponsor, investigators, and study subjects are not blinded in this study. However, to minimize the potential bias associated with assessment of treatment outcome, evaluation for response may be performed by a blinded independent central reviewer. The specific process used for handling test samples and reports will be described separately.

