- ^d **Study treatment:** For details on all treatment regimens, see Section 7.0. TC duration will be based on approved prescribing information and institutional standard practice. For the TC arm, small variations of dose, schedule, route, duration of treatment, and dose adjustment guidelines are allowed as long as they follow the locally approved prescribing information or institutional standard practice and are documented in the eCRF. BSC subjects are to follow the same 28-day cycle schedule as other subjects, despite not receiving cyclical treatment. Treatment delays are permitted to allow normal hematological count recovery in the absence of PB blasts at the investigator's discretion. Delays due to logistical reasons should be limited to 7 days.
- ^e Guadecitabine treatment: Cycle 1 will be on Days 1-5 and 8-12 or Days 1-10 (10-day regimen). Cycle 2 will be either the 10-day regimen or the 5-day (Days 1-5) regimen, based on assessment of disease response and hematological recovery by Day ≥28, as specified in Section 7.1.2. Cycle 3 will be the 5-day regimen (Days 1-5).
- ^f Screening (and Randomization): Screening must occur within 14 days before randomization, except that BM aspirate/biopsy may be collected within 28 days before Cycle 1 Day 1. Cytogenetics should be prior to randomization and may be more than 14 days prior to randomization (see Appendix 3 for cytogenetics-based risk classification). Randomization should occur as close as possible to Cycle 1 Day 1 and may occur on Cycle 1 Day 1. The time between randomization and first treatment should not be more than 1 week.
- ^g **Physical examination:** Includes weight and examination of body systems according to institutional standards. A complete physical examination is required. Cycle 1 Day 1 physical examination does not need to be repeated if it was done at screening within 4 days of Cycle 1 Day 1.
- ^h Vital signs: Assess before dosing on every dosing day in the clinic (based on the subject's assigned treatment regimen), after subject has rested in the sitting position for at least 3 minutes. Subjects in BSC arm: After screening, assess vital signs on Day 1 of every cycle, and at the safety follow-up visit. Vital signs include blood pressure (systolic/diastolic), respiration rate, heart rate, and body temperature. If dosing is done at home (according to local standards), vital signs assessment is not required.

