- ⁱ **12-Lead ECG (triplicate):** Conduct predose and 1-2 hours postdose only on Day 1 of Cycle 1, and at safety follow-up visit. Subjects in BSC arm: Conduct ECG (in triplicate) on Cycle 1 Day 1, and at the safety follow-up visit. Acquire and review according to institutional procedure (rhythm, atrial rate, ventricular rate, PR interval, QRS duration, and QT/QTc, morphology and overall interpretation). The QT correction method should be the same for all ECGs for a given subject. Clinically significant abnormal ECG at study treatment discontinuation as compared to the predose ECG should be followed for recovery or stabilization.
- ^j Health-related QOL: Administer EQ-5D-5L and EQ VAS before treatment on Day 1 of each cycle for 6 cycles, then at every study visit until disease progression. For subjects who discontinue treatment before Cycle 6, administer EQ-5D-5L and EQ VAS monthly until 6 months after the start of study treatment, then at every study visit until disease progression.
- k Weight and BSA calculation: Weigh subjects on Day 1 of each cycle. BSA recalculation is only required if weight changes ±10% or more from the last calculation.
- ¹ Concomitant medications: Document all medications taken within 14 days before randomization to 30 days after the last dose of study treatment, or start of new anti-leukemic treatment for AML (except for hydroxyurea as specified in Section 7.4.1), whichever is first.
- ^m Hematology: Include complete blood count with WBC differential (a manual count should be conducted if there is suspicion of PB blasts). Day 1 hematology for all cycles does not need to be repeated if done within 4 days of Day 1. Additional hematology assessment may be done for safety or for subject management at the investigator's discretion. Collection, analysis, and reporting information are described in the Study Laboratory Manual.
- ⁿ Serum chemistry: Refer to Table 8. Day 1 chemistry for all cycles does not need to be repeated if done within 4 days of Day 1. Additional chemistry assessment may be done for safety or for subject management at the investigator's discretion. Collection, analysis, and reporting information are described in the Study Laboratory Manual.
- Pregnancy test: Women of child-bearing potential only. The screening test must be done within 7 days of Cycle 1 Day 1 (ie, Day -7 to -1); test not required on Cycle 1 Day 1 if done at screening.

r

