7.3.4 Subgroup Analysis

Subgroup analyses will be performed to explore how the treatment effect on OS is influenced by baseline variables, extent of treatment received, and the individual TC therapy administered. To evaluate the treatment effect at different levels of each of these variables, the Kaplan-Meier analysis and Cox model will be performed separately by each level of each variable as follows:

- Age ($<65, \geq 65$).
- Age ($<75, \geq 75$).
- Sex (Male, Female).
- Baseline cytogenetic risk (poor-risk, others).
- Baseline ECOG performance status (0-1, 2).
- Response to initial intensive induction therapy (refractory, first relapse, >1 relapse).
- Prior HCT (yes, no).
- Baseline BM blasts ($\leq 40\%$, >40%).

- Baseline PB blasts ($\leq 30\%$, >30%).
- Baseline total WBC counts ($\leq 20,000/\mu$ L, $> 20,000/\mu$ L).
- Study center region (North America, ROW).
- Race (White, Black, Asian, Other).
- Presence of baseline genetic mutations or gene expressions for each gene such as FLT3-ITD, NPM1, CEBPA biallelic, TP53, ASXL-1, and RUNX-1 (yes, no).
- Treatment cycles received (<4 cycles vs \geq 4 cycles).
- Treatment cycles received (<6 cycles vs \geq 6 cycles).
- Individual preselected TC (high intensity, low intensity, BSC).

The treatment effect (HR and 95% CI) for each of these subgroups will be displayed on Forest plots.

Subjects with missing a value for a variable used to define a subgroup will be excluded from that subgroup analysis except for subgroups with an "Other" category. In those subgroups, subjects with missing values will be included in the Other category.

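### SAP 7.0 ties baseline to Cycle 1 Day 1, which can fall up to 7 days after open-label randomization, so the baseline-ECOG subgroup can be formed after the arm is known and can differ from the ECOG stratum in the primary test

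*SAP*

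**What the plan says.** SAP Section 7.0 gives three baseline rules.

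- General rule: "The baseline value for a particular variable is generally the last value collected prior to the Cycle 1 Day 1 (C1D1) study visit".
- Variables measured on C1D1 itself: "For variables collected on Day 1 of Cycle 1 (C1D1) without explicit timing, the C1D1 values will be used as the baseline values". The stated reason is that the protocol has these tests done before dosing.
- Untreated subjects: "For subjects who were randomized but did not receive study treatment, the baseline value is defined as the last value collected prior to randomization".

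On timing, Protocol 6.1 allows a "maximum of 1 week between randomization and treatment". The notes to the schedule of events (Protocol 9.5.1) add: "Randomization should occur as close as possible to Cycle 1 Day 1 and may occur on Cycle 1 Day 1". Protocol 6.2 states: "The sponsor, investigators, and study subjects are not blinded in this study".

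The schedule of events places ECOG and hematology at screening and again on Day 1 of Cycle 1. Day 1 hematology may be skipped if a result exists within 4 days; ECOG has no such waiver. EQ-5D has no screening administration. The instruction is "Administer EQ-5D-5L and EQ VAS before treatment on Day 1 of each cycle for 6 cycles".

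SAP 7.3.4 lists the OS subgroup "Baseline ECOG performance status (0-1, 2", and further subgroups by baseline WBC and baseline PB blasts. SAP 7.3.2.10 uses the EQ-5D baseline both in the change score and as a model covariate. SAP 7.3.1 stratifies the primary log-rank test and the Cox model by the randomization factors, of which ECOG is one.

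**The concern.** A subgroup variable should be fixed before assignment, so that the arms are comparable within each level. The SAP's justification, that C1D1 values are pre-dose, guards against a drug effect on baseline. It does not guard against knowledge of the arm.

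ECOG is the variable most exposed. It is an investigator's rating, it is repeated at C1D1 without a waiver, and the rater may already know the assignment. If re-rating differed by arm, the ECOG 2 subgroup would mix different kinds of subject in the two arms, and the forest plot could show a subgroup effect that is not there. The confidence interval would not reveal this.

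There is also an inconsistency in terms. SAP 3.1 describes the stratification factors, ECOG among them, as measured at baseline, and these are fixed by randomization. SAP 7.0 can give baseline ECOG a later date. SAP 7.3.4 does not say which source forms the subgroup, so a subject could be ECOG 0-1 in the primary test and ECOG 2 on the forest plot.

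The rule also depends on whether the subject was treated, which is itself a post-randomization event.

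**Working it through.** The plan gives no figure on this point, so there is none to reproduce. The check compares dates and then tests sensitivity.

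**Timing.** Randomization may be on C1D1 (gap 0 days) or up to 1 week before treatment (gap 7 days). A C1D1 value is therefore taken 0 to 7 days after randomization, or before it if the assessment comes first on the same day.

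**By variable.**

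| Variable | Screening value scheduled | C1D1 value scheduled | Can baseline post-date assignment? |
|---|---|---|---|
| ECOG | yes | yes, no waiver | yes |
| WBC, PB blasts | yes | yes, waived if done within 4 days | sometimes |
| EQ-5D | no | yes, first administration | yes; no earlier scheduled value exists |
| BM blasts | yes | no | not through the C1D1 rule |

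**ECOG subgroup, illustration.** Assumptions not taken from the documents: a true HR of 1, exponential survival with medians of 5.0 months (ECOG 0-1) and 2.5 months (ECOG 2), and a share q of TC subjects with ECOG 0-1 re-rated to 2 with their risk unchanged, none in the guadecitabine arm. The share with ECOG 2, p = 14%, is the Phase 2 figure in Protocol Table 1.

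Mislabelled share of the TC ECOG 2 subgroup: m = q(1 − p) / [p + q(1 − p)].

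Mean survival is twice as long for the mislabelled subjects, so with complete follow-up the ratio of event rates (guadecitabine/TC) is (1 − m) + 2m = 1 + m.

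- q = 0: m = 0, ratio 1.00.
- q = 5%: m = 0.043 / 0.183 = 0.235, ratio 1.24.
- q = 10%: m = 0.086 / 0.226 = 0.381, ratio 1.38.

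Hazards within the mixed TC group are not proportional to those in the other arm, so a Cox model gives slightly less. Large-sample simulation with these inputs gives Cox HRs of about 1.22 and 1.34.

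If re-rating is equal in both arms, the two subgroups have the same mixture and the expected HR is 1. If every subject is assessed before being randomized on C1D1, q = 0.

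**Set against sampling error.** With about 300 randomized, ECOG 2 holds about 300 × 0.14 = 42 subjects. Re-rating at 5% adds about 150 × 0.86 × 0.05 = 6, giving about 48. Assuming 45 deaths, SE(log HR) ≈ 2/√45 = 0.30, and the 95% interval around 1.22 is about 0.68 to 2.19.

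**EQ VAS.** If knowing the arm shifted the baseline by d points in one arm, and β is the slope of later score on baseline, the adjusted difference moves by β × d. For assumed d of 2 to 5 and β of 0.3 to 0.7, that is 0.3 × 2 = 0.6 to 0.7 × 5 = 3.5 points.

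**The case against.** The strongest reply is that a pre-dose baseline is a defensible choice with a stated reason, and that it is fresher than a screening value in a fast-moving disease. One week is a ceiling: the protocol asks for randomization as close to C1D1 as possible. The subgroups are exploratory, EQ-5D is outside the testing hierarchy, and no hierarchical endpoint is analysed with a C1D1 covariate. The illustrated bias rests on a one-sided re-rating rate that the documents do not supply, and it lies well inside the noise of a subgroup of about 42 to 48 subjects. A separate rule for untreated subjects is a natural fallback.

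Most of this stands, and it limits the point to secondary analyses. It does not answer the central issue: a pre-randomization ECOG exists for every stratified subject, and the SAP does not say that the subgroup uses it.

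A reader might infer more than the documents support:

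- That baseline values *are* post-randomization. They can be. Same-day randomization is allowed, and WBC and PB blasts may predate randomization under the 4-day waiver.
- That hydroxyurea given only in the TC arm distorts baseline WBC. Protocol 7.4.1 also allows it after randomization in the guadecitabine arm.
- That an eligible subject would be reported as ineligible. SAP 7.1 summarizes eligibility characteristics from screening, and the analysis set excludes nobody for protocol violations.
- That the BM-blast subgroup is affected. No marrow is scheduled at C1D1.

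**Conclusion.** The point holds in a limited form. In SAP 7.0 nothing requires a treated subject's baseline to precede randomization. In an open-label trial with a gap of up to 7 days, baseline ECOG can therefore be rated with the arm known, and WBC and PB blasts can sometimes be measured then. The ECOG subgroup can differ from the ECOG stratum in the primary test.

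The primary OS test, its stratified Cox model and the hierarchical endpoints are not affected. What is exposed is the exploratory OS subgroups, the baseline tables and the supportive EQ-5D analysis.

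The documents do not allow the size to be estimated. An ECOG 2 subgroup HR of about 1.2 to 1.3 under a true HR of 1 requires 5 to 10% one-sided re-rating in the TC arm and a twofold survival difference by ECOG. The bias is zero if re-rating is equal or if randomization follows assessment on C1D1. For EQ-5D the cause is the visit schedule, so disclosure is all that the SAP can offer. Untreated subjects have no scheduled EQ-5D value before randomization, so the SAP rule leaves them without a baseline.

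**What to change.** In SAP 7.0, separate two uses of baseline.

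1. For OS subgroups and baseline tables, define baseline for all randomized subjects, treated or not, as the last value on or before randomization where one exists (ECOG, WBC, PB blasts).
2. In SAP 7.3.4, state that the ECOG subgroup is formed from the randomization stratum, so that it matches the primary test.
3. Keep the pre-dose C1D1 reference for safety shifts and change-from-baseline summaries.
4. For EQ-5D, report by arm how many baselines post-date randomization, and state that untreated subjects have no scheduled baseline.

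The cost is SAP wording and one derivation rule. No new data are needed, and alpha, power and the event count do not change. The drawback is that subgroup values may be up to about 2 weeks old at randomization, because screening may take place up to 14 days before it.
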